2 STUDY DESIGN AND FLOW

2.1 Study design

This is a Phase 2b, multicenter, randomized, double-blind, placebo-controlled, parallel group study to evaluate the efficacy, safety, and tolerability of cenerimod in subjects with moderate to severe SLE.

Approximately 325 adult subjects with SLE will be randomized in a 1:1:1:1:1 ratio to placebo, 0.5, 1, 2, or 4 mg once daily of cenerimod, in addition to background SLE therapy.

Once randomized, all subjects will enter a 6-month double-blind study treatment period defined as Treatment Period 1 (TP1).

Subjects randomized to, and still receiving, placebo, 0.5, 1, or 2 mg at Month 6 will continue their study treatment up to an additional maximum of 6 months in Treatment Period 2 (TP2), for a total maximum of 12 months.

Subjects randomized to the 4 mg arm will receive study treatment at this dose for a maximum of 6 months in TP1. Afterwards, subjects in this group, still receiving this dose

at Month 6, will be re-randomized in a 1:1 ratio to placebo or cenerimod 2 mg to enter TP2 and will continue for a total maximum of 12 months

Subjects who discontinue treatment in TP1 will continue study FU, performing study assessments, up to maximum duration of 12 months.

At EOT, subjects will enter a 6-month FU period (4-month before protocol Version 5).

Treatment allocation is stratified by dose of OCS at Randomization (two strata: < 7.5 mg/day or ≥ 7.5 mg/day prednisone or equivalent), and by disease activity at Screening (with two strata: mSLEDAI-2K < 10 or ≥ 10).

The study will be conducted at approximately 180 sites in 21 countries notably from the regions of Asia Pacific, Eastern Europe, Latin America, North America, and Western Europe.

No interim analysis is planned. There will be three study analyses: the Month-6 analysis, the Month-12 analysis and the final EOS analysis. Month-6 analysis will be performed when all randomized subjects have completed TP1 or discontinued the study. Month-12 analysis will be performed when all randomized subjects have completed TP2 or discontinued the study. Final EOS analysis will be performed when all randomized subjects have completed the post-treatment follow-up period or discontinued the study.

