5 GENERAL DEFINITIONS AND DERIVATIONS

5.1 Study dates

The **'Date of informed consent'** is defined as the date at which the informed consent is signed by the subject. This date is collected on the Informed Consent eCRF page.

The **'Screening date'** is defined as the date where the subject was screened (visit date from IXRS subject eCRF page). If the subject was screened multiple times, the date of last screening attempt will be used.

The **'Randomization date'** is defined as the date when the subject was randomized to one of the four doses of cenerimod or placebo (at the start of TP1) and is taken from the IXRS subject eCRF page.

The **'Re-randomization date'** is defined as the date when the subject was re-randomized through the IXRS system. The re-randomization date is taken directly from this system. The re-randomization date will be populated for subjects who reach the Month 6 visit (on treatment) and are re-randomized.

Note: Subjects on 4 mg are re-randomized to placebo or 2 mg cenerimod in TP2. All other subjects are re-randomized to their original randomized group from TP1.

Definition of treatment start/end dates in TP1

- The **'Treatment start date (TP1)'** is defined as the date of the first study drug intake in TP1 (cenerimod or placebo), as documented in the eCRF Study Treatment Intake.
- The **'Treatment start time (TP1)'** is defined as the time on the date of the first study drug intake in TP1 (cenerimod or placebo), as documented in the eCRF Study Treatment Intake.
- The **'Treatment end date (TP1)'** is defined as the date of the last study drug intake in TP1 (cenerimod or placebo), as documented in the eCRF Study Treatment Log.

Definition of treatment start/end dates in TP2

Treatment start and end dates are defined in the same way as described for TP1.

Due to the start of a conflict in Ukraine around the same time as the planned EOT of several subjects in this country, sites had to stop their activities before entering the treatment end date for TP2 in the eCRF. This concerns a maximum of 9 subjects. For these subjects, the missing treatment end date for TP2 will be imputed at the start date of Month-12 visit. NB: This date is identical to the treatment completion date entered in the IRT system, except for one subject for whom it is the day after.

Overall EOT date

A subject's overall EOT date is defined as the latest of **Treatment end date (TP1)** and **Treatment end date (TP2)**.

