5.6 Other derivations

The following conversion factors will be used to convert days into months or years: 1 month = 30.44 days, 1 year = 365.25 days. For time windows calculation, 1 month is expressed as 30 days.

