8.2.1 Variables

AEs are classified as ‘Treatment-emergent AEs’ if the start date of the AE is on or after the date of first study drug intake (by time and date) up to EOT + 180 days (inclusive).

AEs with onset during TP1 are defined in the interval:

[First study drug intake (by time and date); Month 6 visit or EOT
(if EOT date is on or before Month 6 visit date)]

AEs with onset during TP2 are defined in the interval:

[Month 6 visit + 1 day; EOT].

Any AE prior to start of treatment (by time and date) in TP1 and AEs 121 days or more after EOT are considered non-treatment-emergent AEs.

TEAEs on Day 1 are reported up to 24 hours after first study drug intake in TP1 and on or after the time of first study drug intake.

TEAEs on the day of re-initiation are defined in the same way, but for the day of the re-initiation.

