8.4.2 Variables

The absolute change and percent change from baseline in laboratory parameters (hematology, blood chemistry, and urinalysis) at each post-baseline analysis visit up to EOS is calculated as follows:

- Absolute change in laboratory parameters = Laboratory value at Visit X – Laboratory value at baseline (TP1)
- Percent change in laboratory parameters = (Laboratory value at Visit X – Laboratory value at baseline [TP1]) / Laboratory value at baseline (TP1) × 100

Absolute and percent changes are also derived based on the TP2 baseline.

Laboratory test abnormalities are defined as summarized in protocol appendix 7, for the following periods:

- During TP1: up to Month 6 for subjects who complete TP1 on treatment and up to EOT for subjects who discontinue study treatment during TP1.
- During TP2: up to EOT.
- Treatment-emergent (combining TP1 and TP2 data): up to EOT + 180 days.

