8.7.1.3 Notable blood pressure abnormalities

8.7.1.3.1 Variables

For SBP and DBP, the occurrence of notable abnormalities (up to EOT + 180 days) is assessed according to the criteria defined in Table 12. Values and changes derived above will be used to characterize abnormalities.

Table 12 Notable abnormalities in blood pressure

Analysis parameter	Analysis criterion
SBP (mmHg)	Value ≤ 90 and decrease ≥ 20 from baseline
	Value ≥ 140 and increase ≥ 20 from baseline
	Value ≥ 160
DBP (mmHg)	Value ≤ 50 and decrease ≥ 15 from baseline
	Value ≥ 90 and increase ≥ 15 from baseline
	Value ≥ 100

DBP = diastolic blood pressure; SBP = systolic blood pressure.

Abnormalities are defined for:

- Treatment-emergent on day of first study drug intake: up to 24 hours after first study drug intake.
- During TP1: up to Month 6 for subjects who complete TP1 on treatment and up to EOT for subjects who discontinue study treatment during TP1.
- During TP2: up to EOT.
- Treatment-emergent (combining TP1 and TP2 data): up to EOT + 180 days.

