FACIT-Fatigue, PGIS-F, PGIC-F, SF-36v2 TM and Lupus QoL				X			X
Echocardiography ⁽⁴⁾							X
Vital signs: SBP/DBP* ^{(6) (7)}		X	X	X	X	X	X
12-lead ECG* ⁽⁷⁾				X			X
Spirometry*				X			X
Ophthalmological examinations							X
OCT							X
Hematology and blood chemistry* ⁽¹⁰⁾		X	X	X	X	X	X
Pregnancy test ⁽¹¹⁾		X	X	X	X	X	X
Urinalysis (dipstick)		X	X	X	X	X	X
SLE biomarkers		X	X	X	X	X	X ⁽¹³⁾
Urine protein-to-creatinine ratio		X	X	X	X	X	X
PK sampling*							X ⁽⁹⁾
Study treatment dispensing/return and accountability		X	X	X	X	X	X
AEs ⁽¹²⁾ / SAEs ⁽¹²⁾		X	X	X	X	X	X

PERIODS	Name	FOLLOW-UP					
	Duration	6 months					
VISITS	Number	15	16	17	17a	17b	18
	Name	FU1	FU2 PHONE CALL	FU3 PHONE CALL	FU3a PHONE CALL	FU3b PHONE CALL	EOS
	Time	1 month after last dose ⁽¹⁶⁾ (±7 days)	2 months after last dose ⁽¹⁶⁾ (±7 days)	3 months after last dose ⁽¹⁶⁾ (±7 days)	4 months after last dose ⁽¹⁶⁾ (±7 days)	5 months after last dose ⁽¹⁶⁾ (±7 days)	6 months after last dose ⁽¹⁶⁾ (±7 days)
SLE and concomitant therapies		X					X
Physical examination ⁽²⁾		X					X
Body weight ⁽³⁾							X
mSLEDAI-2K, BILAG, PGA, SFI		X					X
FACIT-Fatigue, PGIS-F, PGIC-F, SF-36v2™, and Lupus QoL							X
Vital signs: SBP/DBP* ⁽⁶⁾⁽⁷⁾		X					X
12-lead ECG* ⁽⁷⁾							X
ECG Holter* ⁽⁸⁾							
Echocardiography ⁽⁴⁾							
Spirometry*							X
Ophthalmological examinations							X
OCT							
PK sampling* ⁽⁹⁾							X

PERIODS	Name	FOLLOW-UP					
	Duration	6 Months					
VISITS	Number	15	16	17	17a	17b	18
	Name	FU1	FU2 PHONE CALL	FU3 PHONE CALL	FU3a PHONE CALL	FU3b PHONE CALL	EOS
	Time	1 month after last dose ⁽¹⁶⁾ (±7 days)	2 months after last dose ⁽¹⁶⁾ (±7 days)	3 months after last dose ⁽¹⁶⁾ (±7 days)	4 months after last dose ⁽¹⁶⁾ (±7 days)	5 months after last dose ⁽¹⁶⁾ (±7 days)	6 months after last dose ⁽¹⁶⁾ (±7 days)
Hematology and blood chemistry* ⁽¹⁰⁾		X					X
Pregnancy test ⁽¹¹⁾		X	X	X	X	X	X
Viral serology / TB test							
Urinalysis (dipstick)		X					X
SLE biomarkers		X					X
Urine protein-to-creatinine ratio		X					X
Study treatment dispensing/return and accountability							
AEs ⁽¹²⁾ / SAEs ⁽¹²⁾		X	X	X	X	X	X

PERIODS	Name	UNSCHEDULED		
	Duration	NA		
VISITS	Number	U1, U2, ...	I1	I2
	Name	Unscheduled ⁽¹⁵⁾	Re-initiation	
	Time	Any day between Day 1 and EOS (assessments to be performed as applicable)	Re-initiating study drug after interruption lasting more than 7 days between Day 1 and Day 14	
SLE and concomitant therapies		X	X	
Physical examination ⁽²⁾		X	X	
Body weight ⁽³⁾		X		
mSLEDAI-2K, BILAG, PGA, SFI		X		

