FACIT-Fatigue, PGIS-F, PGIC-F, SF-36v2™, and Lupus QoL		X		
Chest X-ray ⁽⁵⁾		X		
Vital signs: SBP/DBP* ^{(6) (7)}		X	X	
12-lead ECG* ⁽⁷⁾		X	X	
ECG Holter* ⁽⁸⁾			X	X
Echocardiography ⁽⁴⁾		X		
Spirometry*		X		
Ophthalmological examinations		X		
OCT		X		
PK sampling* ⁽⁹⁾			X	

PERIODS	Name	UNSCHEDULED		
	Duration	NA		
VISITS	Number	U1, U2, ...	I1	I2
	Name	Unscheduled ⁽¹⁵⁾	Re-initiation	
	Time	Any day between Day 1 and EOS (assessments to be performed as applicable)	Re-initiating study drug after interruption lasting more than 7 days between Day 1 and Day 14	
Hematology and blood chemistry* ⁽¹⁰⁾		X		
Pregnancy test ⁽¹¹⁾		X		
Viral serology / TB test		X		
Urinalysis (dipstick)		X		
SLE biomarkers		X		
Urine protein-to-creatinine ratio		X		
Study treatment dispensing/return and accountability			X	
AEs ⁽¹²⁾ / SAEs ⁽¹²⁾		X	X	

One month is considered to be 30 days.

Day 1 (date of Randomization visit) is to be used as the reference date for the purpose of calculating the subsequent visit dates (and time windows).

For WOCBP, the serum pregnancy test at Visit 1 must be performed at least 3 weeks before the urine pregnancy test performed at Visit 2 prior to Randomization.

* Study treatment should not be taken before the assessment (i.e., SBP/DBP, ECGs, spirometry, laboratory tests, and PK sampling).

- (1) Prior to Randomization, the following central laboratory results must be available to confirm eligibility: ANA, anti-dsDNA, anti-HAV IgM, Hepatitis B surface antigen, Hepatitis C antibodies (anti-HCV IgG or IgM), anti-HEV IgM and/or IgG, HEV-RNA PCR (as needed), HIV1 and HIV2, varicella-zoster virus IgM antibody, urine protein-to-creatinine ratio, ALT/AST/TBIL and pregnancy test (if applicable).
- (2) A complete physical examination (i.e., inspection, percussion, palpation, and auscultation) will only be performed at Visits 1, 2, 3, 5, 8, 11, 14, and 15. For all other visits, a symptom-driven abbreviated physical examination will be performed in order to capture assessments needed for the SLEDAI-2K, the PGA, the BILAG, and the SFI.
- (3) Height only at Screening. Body weight should be measured as part of BILAG assessment at each applicable visit and recorded in the source documentation. If clinically relevant, body weight collected outside Screening, EOT and EOS visits may be reported as an Unscheduled assessment.

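### The treatment-emergent window for laboratory, spirometry, ECG and blood pressure abnormalities closes at the centre of the EOS visit window, so on-time EOS values on Days 181 to 187 are not counted

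*SAP*

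**What the plan says.** **The cut-off.** SAP 8.4.2 (laboratory) defines the combined period as "Treatment-emergent (combining TP1 and TP2 data): up to EOT + 180 days". The same line appears in 8.5.2.3 (spirometry), 8.6.2.2 (notable ECG abnormalities), 8.6.2.3 (morphological ECG findings) and 8.7.1.3.1 (blood pressure). The limit is repeated in 8.4.3 and in the opening sentence of 8.7.1.3.1. Only the AE rule in 8.2.1 says that the last day counts: "up to EOT + 180 days (inclusive".

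**The anchor.** Section 5.1 makes the treatment end date of each period the date of last study drug intake. A subject's "overall EOT date is defined as the latest of" the two.

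**The EOS visit.** Appendix 12.1 places EOS "6 months after last dose", with a tolerance of 7 days either way. Note 16 limits that timing to subjects who completed TP2 on schedule. The appendix adds that "One month is considered to be 30 days", and section 5.6 agrees: "For time windows calculation, 1 month is expressed as 30 days".

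**What is measured in follow-up.** Appendix 12.1 has laboratory tests and blood pressure at FU1 and EOS, and 12-lead ECG and spirometry at EOS only. FU2, FU3, FU3a and FU3b are telephone contacts.

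**Counting.** Sections 8.4.3, 8.6.3.1 and 8.7.1.3.2 base percentages on subjects at risk with at least one post-baseline value. Section 8.5.3 gives no denominator for spirometry, so the default in section 9.1 (all subjects in the analysis set) applies.

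**The concern.** A cut-off that coincides with the target day of a scheduled visit makes inclusion depend on the appointment. Two subjects with the same new finding, both seen within the permitted window, are classified differently if one attends on Day 180 and the other on Day 183. The second stays in the denominator and, if the finding is new, is counted as not having had it. This can only lower the reported incidence.

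The visit concerned matters for late safety. For subjects who complete TP2, EOS is the only scheduled follow-up visit with ECG and spirometry, and the only one after FU1 with laboratory tests and blood pressure. The revision history (12.5, version 5.0) says that the treatment-emergent period was updated, for abnormalities and findings as well as AEs, because of evidence for a longer half-life. The period now reaches the one late visit that carries these measurements, but covers only part of its window.

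**Working it through.** **Inputs**
- Cut-off: EOT + 180 days (8.4.2, 8.5.2.3, 8.6.2.2, 8.6.2.3, 8.7.1.3.1).
- EOS target: 6 months after last dose, tolerance 7 days either way (Appendix 12.1).
- Month length: 30 days (Appendix 12.1 and 5.6).
- EOT: date of last intake (5.1), assumed to be the EOT meant in section 8.
- Day 180 included: stated for AEs only (8.2.1), assumed here for abnormalities.
- Distribution of actual EOS days: not given in the documents, so a range is shown.

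**Step 1: target day against cut-off.** 6 × 30 = 180. The EOS target and the cut-off are the same day, counted from the same date.

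**Step 2: permitted days.** 180 − 7 = 173 and 180 + 7 = 187, which is 15 days. Days 181 to 187 lie outside the cut-off: 7 of 15 = 46.7% of permitted days.

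**Step 3: is there a rule that brings these values back?** Table 4 (5.4.4) ends with Month 12 at Day 375 and has no follow-up or EOS row. No other rule in section 8 does so.

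**Step 4: share of visits.** For any distribution of visit days symmetric about Day 180, the share outside is (1 − p)/2, where p is the proportion of visits exactly on Day 180.

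| Visit days within 173 to 187 | p | Share outside |
|---|---|---|
| Even | 1/15 = 6.7% | 46.7% |
| Triangular, weights 8 − distance from Day 180 | 8/64 = 12.5% | 43.8% |
| Discretised normal, SD 3 days | 13.5% | 43.3% |
| Discretised normal, SD 2 days | 20.0% | 40.0% |
| Discretised normal, SD 1 day | 39.9% | 30.1% |

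The share is higher if visits tend to run late and lower if they tend to run early.

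**Step 5: other readings of the rule**
- Day 180 excluded: 8/15 = 53.3%.
- EOS counted from an EOT visit held one day after the last dose (window 174 to 188): 8/15 = 53.3%.
- A 30.44-day month: 6 × 30.44 = 182.6, centre 183, window 176 to 190, so 10/15 = 66.7%. The appendix's own 30-day statement argues against this reading.

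**Step 6: who is affected.** Section 2.1 says that follow-up was 4 months before protocol Version 5. Those subjects have EOS by Day 120 + 7 = 127, always inside the cut-off. If a fraction f of subjects has 6-month follow-up and visits are evenly spread, the share over all subjects is f × 46.7%: 11.7% for f = 25%, 23.3% for 50% and 35.0% for 75%. The documents do not give f.

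**The case against.** The strongest reply is that little is lost and that the single limit is deliberate.

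- **The data are kept.** A reader might infer that nearly half of EOS assessments are thrown away. The documents do not support that. Laboratory and spirometry changes are summarised up to EOS (8.4.2, 8.5.3), 8.1.1 lists ECG and blood pressure changes up to EOS, and all these data are listed. Section 8.6.3.1 also flags notable post-treatment ECG abnormalities. Only the treatment-emergent counts are affected. This stands.
- **The 47% is a share of days.** It becomes a share of visits only if visits are evenly spread, which the documents do not say. This stands, hence the range.
- **EOS is not everyone's only off-treatment measurement.** Subjects who stop early continue their planned visits (2.3.2, Appendix 12.1 note 14), which can include laboratory tests, blood pressure, ECG and spirometry within 180 days of EOT. This stands, and limits the point to subjects who complete TP2.
- **Few counts may change.** For the graded laboratory and ECG criteria, a subject is counted once, in the worst category (8.4.3, 8.6.3.1). In every domain a count changes only if the abnormality first appears, or first reaches a worse category, at an EOS visit on Days 181 to 187. The rule is the same in every arm, and no efficacy result or hypothesis test depends on it. This stands. The documents allow no estimate of the number of events.
- **One limit for all domains is consistent.** AEs are collected up to 6 months after stopping (Appendix 12.1 note 12), so 180 days everywhere has a logic. This stands only in part. AE onset can be dated to any day, whereas these abnormalities are observed only when the visit takes place. A limit at the visit's target day therefore splits on-time visits in a way that it does not split AE onsets.

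**Conclusion.** The point holds for subjects on 6-month follow-up who complete TP2. Their treatment-emergent abnormality window ends on the target day of EOS, so values from 7 of the 15 permitted days are left out of the counts while the subject stays in the denominator. About 30% to 47% of their EOS visits are affected if visits are even or cluster on Day 180. The lower figure corresponds to about 40% of visits falling exactly on Day 180. The share is zero for subjects who finished under the 4-month follow-up.

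The conclusion rests on the 30-day month, the last-dose anchor and Day 180 being included. Any loss is of late first or worsening abnormalities in descriptive safety tables. It is worth correcting before the tables are produced, but it does not bear on efficacy.

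**What to change.** For the scheduled-assessment domains, replace the limit with: up to EOT + 187 days (inclusive). Make the change in 8.4.2, 8.4.3, 8.5.2.3, 8.6.2.2, 8.6.2.3 and 8.7.1.3.1 (both mentions there). Omitting 8.4.3 would leave two different limits for laboratory abnormalities. Stating that the last day counts also settles what is now explicit only for AEs. With the window at 173 to 187, none of the 15 permitted days then falls outside. If a site counts from an EOT visit one day after the last dose, 1 of 15 (Day 188) still would.

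Leave AE onset at 180 days. Section 8.2.1 also treats AEs from 121 days after EOT as non-treatment-emergent. That is a separate inconsistency to be reconciled on its own.

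**Cost.** No new data are needed. Up to 7 more off-drug days are called treatment-emergent, and the abnormality window becomes 7 days longer than the AE window, which a table footnote should state. Section 2.3.3 lets EOS fall later than 6 months after EOT for subjects who stop before Month 8. Their EOS visits well after Day 187 would remain outside the counts.

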8.4.3 Analysis

Laboratory parameters will be summarized using the SAF (for TP1 and for TP1+TP2 combined) and using the SAF-TP2 (for TP2) by visit and treatment group [as defined in Section 5.4.3]. Data will be displayed in SI units as provided by the central laboratory.

Treatment-emergent marked laboratory abnormalities (up to EOT + 180 days) as well as marked laboratory abnormalities during TP1 and during TP2 will be summarized by treatment group.

A subject will be counted only once in the most severe category of a given parameter. However, it is possible that, for a given parameter, the same subject is counted as a high marked abnormality for an observed value and as a low marked abnormality for a different

observed value. An abnormality is only counted as treatment-emergent if the criterion itself and all more severe criterion for the same parameter were not already present at baseline.

Percentages will be based on the number of subjects at risk, i.e., those not meeting the criterion or a more severe criterion for the same parameter at baseline (or having a missing baseline value) and having at least one post-baseline value for a given parameter. For criteria that are not only based on absolute values but also on changes from baseline, subjects with a missing baseline value are not included in the number of subjects at risk.

A standard laboratory listing will be produced using the SAF containing all central and local laboratory data collected in the database. Local laboratory data will only be listed.

8.5 Spirometry

Spirometry measurements are performed every three months during the double-blind study treatment period and at the EOS visit.

Spirometry test results will be transferred from a vendor including information on the quality of the measurements.

A time window approach will be applied to the spirometry data [as defined in Section 5.4.4].

8.5.1 Measurements

FEV₁ (in L) and FVC (in L) are assessed in this study.

The percent predicted FEV₁ and FVC is computed based on the formula defined by Quanjer [Quanjer 1993].

8.5.2 Variables

8.5.2.1 Definition absolute change and percent change from baseline (TP1)

The absolute change from baseline for FEV₁, FVC, percent predicted FEV₁ and percent predicted FVC is calculated as follows:

- Change from baseline = FEV₁ at post-baseline visit – FEV₁ at baseline
- Change from baseline = FVC at post-baseline visit – FVC at baseline

Percent change from baseline for FEV₁, FVC, percent predicted FEV₁ and percent predicted FVC is calculated as follows:

- Percent change from baseline = (FEV₁ at post-baseline visit – FEV₁ at baseline) / FEV₁ at baseline × 100
- Percent change from baseline = (FVC at post-baseline visit – FVC at baseline) / FVC at baseline × 100

Percent change from baseline expressed as percent of predicted baseline for FEV₁ and FVC is calculated as follows:

- Percent change from baseline = $(\text{FEV}_1 \text{ at post-baseline visit} - \text{FEV}_1 \text{ at baseline}) / \text{predicted FEV}_1 \text{ at baseline} \times 100$
- Percent change from baseline = $(\text{FVC at post-baseline visit} - \text{FVC at baseline}) / \text{predicted FVC at baseline} \times 100$

